8.2 Analysis Plan of Year 2 Component D

HAI antibody titers will be compared between groups receiving the mRNA COVID-19 and cclIV4 influenza vaccines concomitantly or sequentially for each of the four influenza vaccine strains contained in the respective vaccines for that season as well as circulating influenza viruses and SARS-CoV-2 variants. Specifically, we will assess the following objectives:

Primary Objective 1a: Compare the proportion of participants in each vaccination group with a seroprotective HAI titer ($\geq 1:40$) pre- and post-cclIV4 immunization for each cclIV4 antigen. These proportions will be compared between vaccination groups using an exact Mantel-Haenszel statistic.

Primary Objective 1b: Compare the proportion of participants in each vaccination group achieving seroconversion following cclIV4 (an HAI titer $\geq 1:40$ following cclIV4 immunization if the baseline titer is $< 1:10$ or a four-fold rise in HAI titer if the baseline titer is $> 1:10$) for each cclIV4 antigen. These proportions will be compared between vaccination groups using an exact Mantel-Haenszel statistic.

Primary Objective 1c: Compare the GMT for each cclIV4 antigen and circulating influenza viruses pre- and post-cclIV4 immunization in each vaccination group. GMT will be compared between vaccination groups using a regression model.

Primary Objective 1d: Compare the GMFR in HAI titer for each vaccination group. GMFR will be compared between vaccination groups using a mixed effects regression model with a random intercept.

Exploratory objectives will be assessed using exact Mantel-Haenszel statistics to compare proportions between vaccination groups, regression models to compare GMT, and mixed effects regression models to compare GMFR. Tables will be provided summarizing counts and proportions for categorical outcomes or summary statistics and confidence intervals for

continuous outcomes. The statistical analysis of each exploratory objective will be fully described in the statistical analysis plan (SAP).

HAI titers will be log transformed prior to analysis and back transformed to estimate GMT and GMFR. The same analysis plan for HAI titers will be repeated for MN titers.

Data analysis will be performed using SAS version 9.4 software (SAS Institute Inc., Cary, NC) or R software (R Core Team, Vienna, Austria).

REFERENCES

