## 6.3 Influenza Immunogenicity Population

The Influenza Immunogenicity Population is a subset of the mITT Population that includes only subjects who received both vaccines, provide visit 1 and visit 2 blood draws available with HAI titer results for analysis within the protocol-defined time frame, did not have an influenza or SARS-CoV-2 infection between visits 1 and 2, and had no protocol violations affecting immunogenicity. Protocol violations affecting the immunogenicity analyses are defined in the Statistical Analysis Plan (SAP) Appendix 1. The acceptable visit window for sample analysis will be +14 days from the target date. Should 10% or more of the total study population be excluded from the Influenza Immunogenicity Population due to missing the visit window, then an additional analysis will be performed including these subjects with the missing visit window exclusion.

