## 6.4 SARS-CoV-2 Immunogenicity Population

The SARS-CoV-2 Immunogenicity Population is a subset of the mITT Population that includes only subjects who received both vaccines, provide visit 1 and visit 2 blood draws available with MSD results for analysis within the protocol-defined time frame, did not have an influenza or SARS-CoV-2 infection between visits 1 and 2, and had no protocol violations affecting immunogenicity. Protocol violations affecting the immunogenicity analyses are defined in the Statistical Analysis Plan (SAP) Appendix 1. The acceptable visit window for sample analysis will be +14 days from the target date. Should 10% or more of the total study population be excluded from the SARS-CoV-2 Immunogenicity Population due to missing the visit window, then an additional analysis will be performed including these subjects with the missing visit window exclusion.

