## 7.1 Multicenter Studies

There are 7 sites participating in the study. Data will be pooled across investigational sites for analysis purposes. A fixed site effect will be included in all analyses of the primary objective.

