## 9 ANALYSIS OF STUDY OBJECTIVES

### 9.1 Primary Objective

The primary objective will be analyzed using the immunogenicity population. All endpoints will be assessed with two-sided tests and alpha set to 0.05.

*Endpoint i:*

The proportion of participants with a seroprotective HAI before and 28-42 days after immunization will be compared between group i (concomitant administration) and ii (influenza administered first), using the following null ( $H_0$ ) and alternative ( $H_1$ ) hypotheses:

$H_0$ : Simultaneous group – Sequential group = 0

$$H_0: \pi_1 - \pi_2 = 0$$

$$H_1: \pi_1 - \pi_2 \neq 0$$

where  $\pi$  is the seroprotective rate.

P values and confidence intervals for the geometric mean titer ratio will be estimated using a logistic regression adjusted for site.

*Endpoint ii:*

The proportion of participants achieving seroconversion will be compared between group i (concomitant administration) and ii (influenza administered first), using the following null ( $H_0$ ) and alternative ( $H_1$ ) hypotheses:

$H_0$ : Simultaneous group – Sequential group = 0

$$H_0: \pi_1 - \pi_2 = 0$$

$$H_1: \pi_1 - \pi_2 \neq 0$$

where  $\pi$  is the seroconversion rate.

P values and confidence intervals for the geometric mean titer ratio will be estimated using a logistic regression adjusted for site.

*Endpoint iii:*

GMTs before and 28-42 days after immunization will be compared between group i (concomitant administration) and ii (influenza administered first), using the following null ( $H_0$ ) and alternative ( $H_1$ ) hypotheses:

$$H_0: \mu_1 / \mu_2 = 1$$

$$H_1: \mu_1 / \mu_2 \neq 1$$

where  $\mu$  is the geometric mean titer.

P values and confidence intervals for the geometric mean titer ratio will be estimated using a generalized estimating equation linear regression accounting for site clustering.

*Endpoint iv:*

Geometric mean fold rise will be compared between group i (concomitant administration) and ii (influenza administered first), using the following null ( $H_0$ ) and alternative ( $H_1$ ) hypotheses:

$$H_0: \mu_1 / \mu_2 = 1$$

$$H_1: \mu_1 / \mu_2 \neq 1$$

where  $\mu$  is the geometric mean fold rise.

P values and confidence intervals for the geometric mean titer ratio will be estimated using a linear regression adjusted for site.

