### *Serology*

Microneutralization (MN), SARS-CoV-2 binding antibody and viral neutralization, and circulating virus objectives will all use the same statistical methods as the primary HAI objective. Waning objectives will use parametric models to estimate the rate of antibody decline by time since vaccination. Estimated GMTs and fold change will be presented for each time point with their associated 95% confidence intervals.

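### The primary HAI models make little or no use of the Visit 1 titre: no bias, but precision is lost, more for GMT (endpoint iii) than for GMFR (endpoint iv)

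*SAP*

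**What the plan says.** SAP 9.1 compares group i (concomitant) with group ii (influenza vaccine first), two-sided at 0.05, for each vaccine antigen.

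- Endpoint iii (GMT): P values and intervals are "estimated using a generalized estimating equation linear regression accounting for site clustering".
- Endpoint iv (GMFR): "P values and confidence intervals for the geometric mean titer ratio will be estimated using a linear regression adjusted for site".
- SAP 7.1, for the whole primary objective: "A fixed site effect will be included in all analyses of the primary objective".
- SAP 10 defines fold rise as the post-vaccination titre divided by the pre-vaccination titre, works on the log2 scale, and sets values below the detection limit to half that limit.

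Neither document names the Visit 1 titre as a covariate. Protocol 8.2 does not supply it either: for objective 1c, "GMT will be compared between vaccination groups using a regression model"; for 1d, "GMFR will be compared between vaccination groups using a mixed effects regression model with a random intercept".

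The baseline is complete by definition. SAP 6.3 admits only participants who "provide visit 1 and visit 2 blood draws available with HAI titer results", and in groups i and ii Visit 1 precedes the influenza vaccine. SAP 6.4 has the same requirement for binding antibody: "provide visit 1 and visit 2 blood draws available with MSD results". Under SAP 9.2 (Serology), the MN, SARS-CoV-2 and circulating-virus endpoints "will all use the same statistical methods as the primary HAI objective".

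**The concern.** Pre-vaccination HAI titre is the obvious predictor of post-vaccination titre, and it is held for every participant in the analysis. Endpoint iii ignores it. Endpoint iv uses it with a slope fixed at 1, which is efficient only if the true slope of post on pre is 1. At stake is precision that needs no new participant or assay. The same loss recurs for four HAI antigens and for each serology endpoint that inherits these methods.

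There is also a matter of agreement between the two outcomes. If the true slope b lies between 0 and 1, a chance baseline difference between groups pushes the unadjusted GMT ratio one way and the GMFR ratio the other. The adjusted model removes this.

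Age group is a lesser omission: it is a randomisation stratum (SAP 4.3) but not a model term.

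**Working it through.** **Inputs.** From the documents: 300 + 100 = 400 randomised to group i and 150 + 50 = 200 to group ii (Protocol Summary). These are maxima, because HAI may be run on a subset. The log2 scale and half-limit rule are from SAP 10. The plan states no SD, correlation, power or precision figure, so there is nothing to reproduce. Assumed: log2 SD 2, GMT 20 before and 80 after, pre/post correlation r = 0.4, 0.5 or 0.7, two-fold dilutions from 1:10, and lower values set to 5.

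**Formulas.** Let s0 and s1 be the pre and post SDs and ρ their correlation after the floor. Per-participant variances, with site as a fixed effect throughout, are:

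- post only: s1²
- change score: s0² + s1² − 2ρ·s0·s1
- baseline-adjusted: s1²(1 − ρ²)

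The cut is ρ² for iii. For iv it is (s0 − ρ·s1)² divided by the change-score variance, which is never negative and is zero when b = ρ·s1/s0 = 1.

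**Worked case, r = 0.5.** After the floor, s0 = 1.65, s1 = 1.95 and ρ = 0.468.

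- Post only: 1.95² = 3.80.
- Adjusted: 3.80 × (1 − 0.219) = 2.97.
- Change score: 2.72 + 3.80 − 2 × 0.468 × 1.65 × 1.95 = 3.51.
- Cuts: 22% for iii and about 15% for iv.

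| r | ρ after floor | slope b | variance cut, iii | interval narrower, iii | variance cut, iv | interval narrower, iv |
|---|---|---|---|---|---|---|
| 0.4 | 0.373 | 0.44 | 14% | 7% | 20% | 11% |
| 0.5 | 0.468 | 0.55 | 22% | 12% | 15% | 8% |
| 0.7 | 0.658 | 0.78 | 43% | 25% | 6% | 3% |

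Without the floor and with equal SDs, the cuts are r² = 16, 25, 49% (iii) and (1 − r)/2 = 30, 25, 15% (iv). The floored figures are the relevant ones, given the half-limit rule.

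**On the ratio scale, r = 0.5.** At 400 vs 200 the unadjusted SE is 1.95 × √(1/400 + 1/200) = 0.169, so the 95% factor is 2^(1.96 × 0.169) = 1.26. Adjusted, the SE is 0.169 × 0.884 = 0.149 and the factor is 1.23. For children alone (100 vs 50) the factor goes from 1.58 to 1.50. For GMFR at 400 vs 200 it goes from 1.247 to 1.225.

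**Chance imbalance.** One standard error of the baseline difference is 1.65 × √(1/400 + 1/200) = 0.143 log2. At b = 0.554 it moves the GMT ratio to 2^(0.554 × 0.143) = 1.056 and the GMFR ratio to 2^(−0.446 × 0.143) = 0.957.

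**Protocol 1d.** With complete pairs, the group-by-visit contrast of a random-intercept model is the change-score contrast. In one simulated data set both were 0.0899 (SE 0.1715), against an SE of 0.150 with baseline adjustment.

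**Bias.** In simulated trials with no true effect (300 vs 150, ordinary regression, site fixed), mean estimates were within 0.005 log2 of zero and type I error was 4.5 to 5.2%, with or without baseline.

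**The GEE in endpoint iii.** The calculations above do not describe it. It was simulated under the null at 400 vs 200 and r = 0.5, with an independence working model, site as cluster, the usual sandwich SE and a 1.96 cut-off. It rejected about 19% of the time with four sites (Protocol Summary) and 13% with seven (SAP 7.1). Adding baseline inside that GEE left 18% and 12%. Ordinary regression with site fixed gave 4 to 5%. With four sites the mean sandwich SE was 0.135 against 0.169, so its printed interval would be too narrow.

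**Age group.** At r = 0.5 without the floor, omitting it leaves the true sampling SD unchanged. For an assumed 1 log2 child-adult difference, it raises the model SE for iii only from 0.173 to about 0.176.

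**The case against.** The strongest reply is that this is an efficiency suggestion, not an error. Unadjusted GMT ratios and GMFRs match the listed outcomes. Every SD, correlation and GMT above is assumed. In the central case the pooled limit moves only from 1.26 to 1.23, and no margin or power target in the documents turns on that. Adjustment also merges the between-group tests of two listed outcomes. All of this is fair and limits the size of the point. What remains is that the covariate is complete, costs nothing to collect, and improved precision at every correlation tried.

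Four stronger readings should be set aside.

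- A reader might infer that omitting baseline biases the comparison or inflates type I error. It does neither: the groups are randomised and the models are linear.
- A reader might infer that both endpoints ignore the Visit 1 titre. Endpoint iv does not, and its interval gain is only 3 to 11%.
- A reader might expect contradictory findings. Under the null, the GMT and GMFR point estimates fall on opposite sides of 1 in 27 to 37% of trials per antigen, but both being significant in opposite directions has probability 0.005% or less.
- In the other direction, a reader might take the absence of bias as assurance that endpoint iii is sound as written. That fails if the GEE uses the usual sandwich SE. The SAP states neither the type of SE nor any small-sample correction.

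**Conclusion.** The point holds as a loss of precision: moderate for endpoint iii and small for endpoint iv. Under the stated assumptions, intervals would be 7 to 25% narrower for GMT and 11 to 3% narrower for GMFR. The GMT gain rises with the pre/post correlation, while the GMFR gain falls. The direction needs no assumed value, since in large samples baseline adjustment is never less precise than either alternative; the size does depend on them. The comparison is between ordinary regressions with site fixed. Whether endpoint iii's test holds its level is a separate matter that depends on the unstated SE of the GEE, and adding baseline does not settle it. The change should be made, but the omission does not by itself invalidate any planned result.

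**What to change.** For the post-vaccination comparison in endpoint iii, and for endpoint iv, prespecify one linear regression per antigen. The outcome is log2 post-vaccination titre (or log2 fold rise). The terms are group, log2 Visit 1 titre for that antigen, site as a fixed effect as SAP 7.1 already states, and age group if the ages are pooled. Use ordinary model-based standard errors. This replaces the site-clustered GEE, and that replacement, not the covariate, is what restores the level of the endpoint iii test.

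Keep by-group GMT and GMFR as listed outcomes. Apply the same model to the serology endpoints that inherit these methods, using the pre-vaccination titre of the same assay and antigen. MN and viral neutralisation are run on subsets, so use participants with both results. Endpoints i and ii need no change on this account.

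The cost is an SAP amendment before HAI results are linked to group, with Protocol 8.2 (1c and 1d) aligned. No new data are needed for HAI or binding antibody. The real downside is that the adjusted GMT-ratio and GMFR-ratio contrasts are numerically identical, so two primary outcomes share one between-group test, and the SAP must say so.

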Study Duration:	12 months total Enrollment: Aug — Oct 2023 Vaccination: Aug — Nov 2023 Blood draws: Aug 2023 — May 2024 Active surveillance for illness: Aug 2023 — May 2024 Laboratory testing: Nov 2023 — Jul 2024
Participant Duration and Number of Participants:	
 • Up to 10 months (Aug 2023 — May 2024) • 800 total participants (600 aged 18-64 years, 200 aged 6-11 years) at 4 sites (only two sites will enroll children aged 6-11 years)
Randomization:	Adults aged 18-64 years, 2:1:1 permuted block randomization 
 i. Concomitant cclIV4 + COVID-19 mRNA (day 0) [n = 300] ii. Sequential cclIV4 (day 0), COVID-19 mRNA (day 28) [n = 150] iii. Sequential COVID-19 mRNA (day 0), cclIV4 (day 28) [n = 150]

	
Children aged 6-11 years, 2:1:1 permuted block randomization
 
 i. Concomitant ccIV4 + Moderna COVID-19 mRNA (day 0) [n = 100] ii. Sequential ccIV4 (day 0), Moderna COVID-19 mRNA (day 28) [n = 50] iii. Sequential Moderna COVID-19 mRNA (day 0), ccIV4 (day 28) [n = 50]

Description of Study Procedures:
	
This study is a randomized immunogenicity study in an enrolled cohort with active surveillance for acute respiratory illness (ARI). During this study, participants will be randomly assigned to receive an approved quadrivalent influenza vaccine (Flucelvax [ccIV4]) and mRNA COVID-19 vaccine (Moderna) either concomitantly (given in contralateral arms) or sequentially (28 days apart).
 
Blood samples from participants will be collected for measurement of biomarkers of immune response at baseline (visit 1; day 0), post-vaccination 1 (visit 2; day 28), post-vaccination 2 (visit 3; day 56), and post-season (visit 4; day 180). Serum and peripheral blood mononuclear cells (PBMC) and plasma (target to collect PBMC and plasma samples at every visit from a subset of approximately 250 participants; 200 adults and 50 children) samples will be isolated from whole blood and tested for biomarkers of vaccine immunogenicity, and duration of antibody responses.

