5 METHODS

5.1 *Main study design*

This study is a randomized comparative immunogenicity study in an enrolled cohort. During this study, participants will be randomly assigned to receive an approved quadrivalent cell culture-based influenza vaccine (cclIV4) and mRNA COVID-19 vaccine (Moderna) either concomitantly or sequentially, 28 days apart. Participants (aged 6-11 years and 18-64 years) will be enrolled in the 2023-2024 influenza season. Only two of the sites (Washington University in St. Louis and University Hospitals Cleveland Medical Center) will enroll children aged 6-11 years. Individuals will be enrolled who have not received their 2023-2024 influenza vaccine and have not received any COVID-19 vaccine in the preceding 6 months (i.e. at least 6 months have passed since their last COVID-19 vaccination).

Participants will be enrolled if one dose of 2023-2024 influenza vaccine and a single booster dose of mRNA COVID-19 vaccine are indicated for current vaccination according to ACIP recommendations. To qualify for the study, children aged 8 years and younger must only need to receive a single dose of cclIV4 per ACIP recommendations for the 2023-2024 season. mRNA COVID-19 vaccines recommended by CDC and/or authorized or approved by the FDA at the time of enrollment may include updated SARS-CoV-2 viral components which may be included in this study if authorized or approved by the FDA and recommended by the CDC.

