## 4.3 Randomization

Permuted block randomization stratified by age group (children aged 6-11 years and adults aged 18-64 years) and site will be used at each site to ensure even allocation to each study arm. At each site, participants will be randomized 2:1:1 to receive: (i) concomitant administration of a mRNA COVID-19 vaccine and a quadrivalent influenza vaccine (cclIV4), (ii) sequential administration of a quadrivalent influenza vaccine (cclIV4) at Visit 1 (day 0) and a mRNA COVID-19 vaccine at Visit 2 (day 28), and (iii) sequential administration of a mRNA COVID-19 vaccine at Visit 1 (day 0) and a quadrivalent influenza vaccine (cclIV4) at Visit 2 (day 28).

The project statistician will generate the randomization schemes which will be uploaded to REDCap. The randomization schedule will not be available to the study staff, so the next randomization allocation will not be known before randomization occurs. Following confirmation of study eligibility criteria during Visit 1, participant randomization will be through REDCap with treatment allocation recorded on the case report form (CRF).

In the event that REDCap is unavailable, participants will be manually randomized through the use of sealed envelopes with randomization allocations enclosed. The project statistician will prepare envelopes that will use the same randomization strategy as the primary scheme embedded in REDCap. When an unblinded team member is informed of the age group, they will pull the next envelope in order. To capture the allocation per subject, a separate form in REDCap will be used by the unblinded study personnel to add the assignment. Sites will need to keep a log capturing these instances. The next available sequential study-number will be assigned to each enrolled participant upon study-entry.

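### Age group is a randomisation stratum, but the primary models contain no age term and no result for children is pre-specified

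*SAP*

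**What the plan says.** The Protocol Summary sets up two age cohorts, 600 adults and 200 children, each with its own 2:1:1 allocation. For the younger cohort it reads "Children aged 6-11 years, 2:1:1 permuted block randomization", with targets of 100, 50 and 50; the adult targets are 300, 150 and 150. SAP 4.3 names both stratification factors: "Permuted block randomization stratified by age group (children aged 6-11 years and adults aged 18-64 years) and site will be used at each site". Protocol 5.1 adds: "Only two of the sites (Washington University in St. Louis and University Hospitals Cleveland Medical Center) will enroll children aged 6-11 years".

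The analysis uses only one of the two factors. SAP 7.1 states: "A fixed site effect will be included in all analyses of the primary objective". In SAP 9.1, endpoints i and ii use logistic regression with site adjustment. Endpoint iii uses a GEE linear regression with site as the cluster. For endpoint iv, "P values and confidence intervals for the geometric mean titer ratio will be estimated using a linear regression adjusted for site". Every endpoint has one contrast, group i against group ii, and "All endpoints will be assessed with two-sided tests and alpha set to 0.05". SAP 9.2 carries the same methods over to the exploratory serology.

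Neither document plans an age term, an age-specific estimate or a group-by-age term. Age is otherwise used only in the disposition flow chart (SAP 8.1) and the demographics table (SAP 8.2). Protocol 8.2 plans an exact Mantel-Haenszel test for the proportions but does not name its strata, so age stratification there is unspecified rather than ruled out. No sentence says outright that children and adults are pooled. That follows from the unsplit contrast and from Protocol 3.2, which combines data across sites into 800 participants for the schedule comparison.

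**The concern.** The protocol title names children and adults as the study population, and the two cohorts do not overlap in age. If giving the vaccines together affects the influenza response differently in children, a single estimate that is three-quarters adult will hide most of the difference, and no planned output would show it. The study is open-label, so an age split added once results are known could be read as post hoc.

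There is a separate efficiency question. When a stratification factor predicts the outcome and is left out of the model, its variance stays in the error term. In a logistic model its omission also moves the odds ratio toward 1.

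**Working it through.** The documents give no SD, effect size or power calculation, so there is no stated figure to reproduce. The arm sizes do follow from 2:1:1: 600 gives 300/150/150 and 200 gives 100/50/50.

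**Inputs from the documents.** Group i: 300 adults, 100 children. Group ii: 150 adults, 50 children. Two-sided alpha 0.05. Titres on the log2 scale (SAP 10). Children at two of four sites, up to 250 participants per site (Protocol 3.2).

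**Assumptions.** SD of log2 titre 1.7, with a range of 1.5 to 2.5. Difference d between age-group means of 1 to 2 log2 units. No exclusions.

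**1. Dilution.** Children's share of groups i and ii = 150/600 = 0.25. Allocation is 2:1 in every stratum, so the linear estimate is the sample-weighted average of the two age-specific effects. With no adult effect and a child ratio of 0.67:
- pooled ratio = 0.67^0.25 = 0.905, that is log2(0.67)/4 = -0.578/4 = -0.144
- pooled SE = SD × sqrt(1/400 + 1/200)
- child SE = SD × sqrt(1/100 + 1/50)
- child 95% CI factor = 2^(1.96 × child SE)

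| SD | pooled SE | pooled z | child SE | child z | child 95% CI factor |
|---|---|---|---|---|---|
| 1.5 | 0.130 | 1.11 | 0.260 | 2.22 | ×/÷ 1.42 |
| 1.7 | 0.147 | 0.98 | 0.294 | 1.96 | ×/÷ 1.49 |
| 2.0 | 0.173 | 0.83 | 0.346 | 1.67 | ×/÷ 1.60 |
| 2.5 | 0.217 | 0.67 | 0.433 | 1.33 | ×/÷ 1.80 |

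For a larger child-only ratio of 2.0, the pooled ratio is 2^0.25 = 1.19. Power, pooled against children alone, is 49% v 97% at SD 1.5, 30% v 82% at SD 2.0 and 21% v 64% at SD 2.5.

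**2. Does site stand in for age?** Two adult-only sites can hold at most 2 × 250 = 500 of the 600 adults, so at least 100 adults must come from the sites that enrol children. The total variance of the age indicator is 0.25 × 0.75 = 0.1875. Two splits that the protocol allows leave this much within sites:
- A: 100 children + 150 adults at two sites, 150 adults at each of the others: (500 × 0.4 × 0.6)/800 = 0.150, or 80% of the total. This is the maximum under the 250 cap.
- B: 100 children + 50 adults at two sites, 250 adults at each of the others: (300 × 2/3 × 1/3)/800 = 0.083, or 44%.

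**3. Precision.** The share of residual variance removed by adding age is v·d²/(v·d² + SD²), where v is the within-site value from step 2. At SD 1.7 (SD² = 2.89):

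| d | split A | split B |
|---|---|---|
| 1.0 | 0.150/3.040 = 5% | 0.083/2.973 = 3% |
| 1.5 | 0.338/3.228 = 10% | 0.188/3.078 = 6% |
| 2.0 | 0.600/3.490 = 17% | 0.333/3.223 = 10% |

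Over SD 1.5 to 2.5 the extremes are 0.083/6.333 = 1% (SD 2.5, d = 1, split B) and 0.600/2.850 = 21% (SD 1.5, d = 2, split A).

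**4. Type I error.** In 20,000 simulated trials of 600 participants (split A proportions, SD 2.0, ordinary linear regression with fixed site effects), adding age changed the SE from 0.176 to 0.173 and the type I error from 4.5% to 4.9% at d = 1. At d = 2 the SE went from 0.186 to 0.173 and the error from 3.6% to 5.1%. Omitting age is therefore conservative. The GEE for endpoint iii was not simulated.

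**5. Odds ratio.** Take a site that is 40% children with a true within-age odds ratio of 2.0. With base rates of 60% in adults and 85% in children (assumed), the control proportion is 0.4 × 0.85 + 0.6 × 0.60 = 0.700 and the comparison proportion is 0.4 × 0.919 + 0.6 × 0.750 = 0.818, so the odds ratio is 4.48/2.33 = 1.92. With 50% and 90% it is 1.82.

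**The case against.** The primary objective asks for no age-specific answer, and Protocol 3.2 can be read as declaring the combined comparison by design. Pooling also has real merit: if the effect is the same at both ages, the pooled analysis is unbiased for the linear endpoints and more powerful (92% against 83% for adults alone, at a ratio of 1.5 and SD 2.0). Nothing in the documents suggests interference confined to children. All of this stands, and it is why the pooled estimate should remain primary.

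A separate analysis of children is no clear rescue either. In the 0.67 example at SD 1.7 its z is only 1.96, with an expected interval of 0.45 to 1.00, so it would reach significance about half the time. Exclusions would lower that, and so would HAI testing confined to a subset of samples, which the protocol mentions without giving a size.

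The precision gain depends on unstated quantities. An age difference in titre level need not carry over to fold rise, which is the endpoint of the quoted sentence. Site adjustment already absorbs 20% to 56% of the age variance under the two splits. SAP 7.1 counts 7 sites where the protocol has four, so the spread of adults is uncertain. The dilution arithmetic does not depend on site.

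On the logistic endpoints, the stated hypothesis is a difference in proportions, which is not subject to this attenuation. The point applies to the odds ratio that the planned model would estimate.

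**Conclusion.** The point holds as an omission that is easily repaired; it does not make the primary analysis invalid. One of two randomisation strata is missing from every primary model, and no estimate for children is pre-specified. If the effect differs by age, a child-only effect shows at a quarter of its log size. That figure rests only on the planned arm sizes and the constant 2:1 ratio. The z values, interval widths and precision gains rest on assumed SDs and age differences.

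A reader might infer that the trial says nothing about children, or that leaving age out biases the test. The documents support neither. Randomisation within age and site makes the pooled linear estimate a valid average that includes children, and the simulated linear test is slightly conservative rather than too liberal. A reader might also infer that an age covariate alone cures the dilution. It does not: power for a child-only ratio of 2.0 at SD 2.0 stays near 30% with age in the model, so separate estimates are needed as well.

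**What to change.** In SAP 9.1 and 7.1, add age group (6-11 v 18-64 years) as a fixed term with site in all four primary endpoint models, and keep the pooled group i v ii estimate as primary. Pre-specify the same contrast with its 95% confidence interval separately for children and for adults, and report the group-by-age term descriptively. Apply the same terms to the exploratory serology in SAP 9.2. If the exact Mantel-Haenszel test in Protocol 8.2 is retained, name its strata.

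No new data or participants are needed. The cost is reporting: 2 age groups × 4 endpoints × 4 antigens = 32 further estimates at one time point, plus 16 group-by-age terms. The children's estimates (at most 100 v 50; 95% CI about ×/÷ 1.49 at SD 1.7, before exclusions) must be labelled as estimates and not read as confirmatory tests.
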